5.3. Safety Definitions

AE or SAE Onset Date

AE and SAE onset or start dates are reported in the AE eCRFs.

AE or SAE End Date

AE and SAE end dates are reported in the AE eCRFs.

AEs and SAEs

AEs will be recorded from the time written informed consent is signed through the Follow-up visit (last dose + 30 days).

An AE or SAE will be regarded as treatment-emergent if it has a start date during or after the first study drug administration or if it worsened or if the relationship to study drug changed from unrelated to related after the first study drug administration. UC disease relapse and related symptoms will be monitored as study endpoints, but will not be recorded as AEs unless they meet the definition of an SAE.

All AEs or SAEs meeting these criteria with a start date up to and including 30 days following the last dose of treatment with the study drug will be considered treatment-emergent.

Treatment Related AEs

For summary purposes, all AEs classified by the Investigator on the AE eCRF as "possible", "probable" or "related" will be considered treatment related AEs. If the relationship to study drug is unknown or missing, the AE will be considered to be treatment related.

Duration of AEs

The duration of an AE will be calculated as:

Duration = (AE End Date - AE Onset Date) + 1

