5.4. Other Definitions

Age

Age (in years) will be calculated from the date of birth to the date of informed consent. Age will be reported as an integer.

Study Drug

Study drug refers to RPC1063 0.5 mg, RPC1063 1.0 mg, or Placebo oral capsules as well as the titration doses.

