6.8. Analysis Populations

The following analysis populations will be used in the statistical analysis. Analysis population membership will be determined prior to unblinding.

Intent-to-Treat (ITT) Population: The ITT population will consist of all randomized patients who received at least 1 dose of study treatment, with treatment assignment designated according to randomized treatment. This will be the primary population for the analysis of efficacy endpoints.

Per Protocol (PP) Population: The PP population will consist of the subset of the ITT population, excluding those patients who have had a major protocol violation. Major protocol violations will include all violations that would significantly impact assessment of safety and efficacy of the compound and will be finalized in advance of data lock and primary analyses. Violation of any of the following three inclusion criteria related to UC specific disease activity would exclude a patient from the PP population:

- Must have a confirmed diagnosis of UC by endoscopic and histologic evidence
- Must have a baseline Mayo score of 6-12 inclusive with endoscopic subscore of >=2
- Must have a baseline endoscopy with >= 15 cm involvement

Poor study drug compliance will also exclude the patient from the PP population. Poor study drug compliance is defined as taking less than 80% or more than 120% of study treatment during the entire treatment period.

The patients excluded from the PP population will be fully defined and documented with reasons for exclusion prior to database lock.

Safety Population: The Safety population will consist of all patients receiving any study treatment. All patients in the Safety population will be analyzed according to the highest dose of RPC1063 actually received and not according to the treatment they are randomized to receive, in the event there is a discrepancy.

6.9. **DMC**

An independent DMC will be charged with monitoring accumulating data from the trial, as well as general aspects of trial conduct.

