6.20.1. Adverse Events

For presentation, adverse event verbatim text will be coded into MedDRA System Organ Class (SOC) and preferred term. For all AE summaries, if a patient has more than one AE within a preferred term, the patient is counted once in that preferred term at the maximum severity and closest relationship to study material or dosing procedure. If a patient has more than one AE within a system organ class, the patient is similarly counted once in that system organ class.

All AE safety summaries by treatment group will separately summarize the incidence of events in the placebo group, each RPC1063 dose group, and RPC1063 dose groups combined.

An overview of AEs will be tabulated by treatment group. The number and percentage of patients in each treatment group will be summarized for the following categories:

- any treatment-emergent AEs
- any SAEs
- treatment-related AEs
- •treatment-related SAEs
- •mild, moderate and severe AEs
- AEs with a start date during IP
- AEs with a start date during MP
- AEs with a start date during OLP
- AEs leading to study discontinuation
- AEs leading to study drug discontinuation

The following AE tables refer to AEs that are reported at any time during the study. The number and percentage of unique patients reporting each treatment-emergent AEs will be summarized by SOC, preferred term, and treatment group. A similar table will also be prepared separately for SAEs. Further, the number of treatment-emergent AEs and SAEs, categorized by SOC, preferred term, maximum severity (mild, moderate, or severe), and treatment group will be summarized. In addition, the number of treatment-emergent AEs and SAEs, categorized by system organ class, preferred term, relationship to study drug, and treatment group will be summarized. Finally, the incidence of AEs by preferred term only will be summarized, sorted by descending frequency in the combined RPC1063 group. All AE tables with both SOC and preferred term will be sorted by SOC alphabetically and then by preferred term in descending AE frequency in the combined RPC1063 treatment group. All of these AE and SAE tables will also be repeated for AEs that are reported with start dates during the IP, during the MP, and during the OLP.

AEs with start dates during a follow-up period will be categorized with the previous study phase.

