4. DMC

2.

There were no DMC reviews planned for the OLP.

5. Patient Disposition

Patient disposition information will only include subjects who participated the OLP.

6. **OLP Baseline**

Baseline for efficacy analyses:

Core baseline: The last assessment prior to/on first dose date in Core Period.

The full set of the efficacy endpoints will be derived based on Core baseline.

Baseline for safety analyses:

The adverse events (AEs) will be summarized per Section 8.

For non-AE safety endpoints, definition of Baseline will not change (SAP v2.0 Section 5.1)

7. Efficacy Analyses

The efficacy measurements will be summarized by parent study treatment group at each OLP visit in the OLP ITT population. Non-responder imputation (NRI) will be used as the primary method for addressing missing binary outcomes. No treatment failure rule will be applied in the OLP, as per its defined in Section 6.19 (SAP v2.0).

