7.3. Visit Windows

Post-OLP-Baseline visits (scheduled or unscheduled) during OLP will be mapped to an analysis visit based on the windowing algorithm below. If a visit cannot be mapped to any analysis visit, then the analysis visit will be set to missing and the data of interest will be excluded from summaries. If multiple visits containing the same data of interest can be mapped to the same analysis visit, the visit closest to the target day will be used in the analysis. In the event that two or more visits are equidistant to the target day, the later visit will be used in the analysis. If the two visits are on the same day, then the visit with the worst result will be used in the analysis.

Visit	Target Day	Analysis Visit Window for partial Mayo score	Analysis Visit Window for Complete Mayo Score, 9-point Mayo Score and Geboes Index
		(+/- 6 weeks)	(+/- 24 weeks)
Day 1OLP	1	N/A	N/A
Week 4OLP	36	(19-50)	N/A
Week 8OLP	64	(51 - 106)	N/A
Week 20OLP	148	(107 - 190)	N/A
Week 32OLP	232	(191 - 274)	N/A
Week 44OLP	316	(275 - 358)	N/A
Week 56OLP	400	(359 - 442)	(232 - 568)
Week 68OLP	484	(443 - 526)	N/A
Week 80OLP	568	(527 - 610)	N/A
Week 92OLP	652	(611 - 694)	N/A

Week 104OLP	736	(695 - 778)	(569 - 904)
Week 116OLP	820	(779 - 862)	N/A
Week 128OLP	904	(863 - 946)	N/A
Week 140OLP	988	(947 - 1030)	N/A
Week 152OLP	1072	(1031 - 1114)	(905 - 1240)
Week 164OLP	1156	(1115 - 1198)	N/A
Week 176OLP	1240	(1199 - 1282)	N/A
Week 188OLP	1324	(1283 - 1366)	N/A
Week 200OLP	1408	(1367 - 1450)	(1241 - 1576)
Week 212OLP	1492	(1451 - 1534)	N/A
Week 224OLP	1576	(1535 - 1618)	N/A
Week 236OLP	1660	(1619 - 1702)	N/A
Week 248OLP	1744	(1703 - 1786)	(1577 - 1912)
Week 260OLP	1828	(1787 - 1870)	N/A
Week 272OLP	1912	(1871 - 1954)	N/A
Week 284OLP	1996	(1955 - 2038)	N/A
Week 296OLP	2080	(2039 - 2122)	(1913 - 2248)
Week 308OLP	2164	(2123 - 2206)	N/A
Week 320OLP	2248	(2207 - 2290)	N/A

8. Safety Analyses

AEs will be recorded from the time written informed consent is signed through the 90-day safety Follow-up visit to ensure adequate collection of adverse events that could be associated with investigational drug.

Treatment-emergent adverse events include adverse events that started between the date of first dose of OLP and 90-day safety Follow-up visit after the date of last dose.

9. Guideline on Missing Date Imputation

The following missing data imputation rules will be applied to the OLP analyses.

Medication Dates:

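### The OLP addendum states only an onset criterion for treatment-emergent AEs, so an AE ongoing at OLP entry that worsens on first or higher RPC1063 exposure goes uncounted in the OLP tables unless recorded as a new AE

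*SAP*

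**What the plan says.** The addendum sends OLP adverse events to its own Section 8: "The adverse events (AEs) will be summarized per Section 8". For the other safety endpoints, the same place (Addendum Section 6) keeps the baseline definition of SAP v2.0 Section 5.1. Section 8 then defines the events to be counted: "Treatment-emergent adverse events include adverse events that started between the date of first dose of OLP and 90-day safety Follow-up visit". It mentions neither worsening nor a change in relationship.

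Core SAP 5.3 has three routes to treatment-emergent status. Besides onset at or after first study drug, an event qualifies "or if it worsened or if the relationship to study drug changed from unrelated to related after the first study drug administration". Core SAP 5.4 fixes what study drug means: "Study drug refers to RPC1063 0.5 mg, RPC1063 1.0 mg, or Placebo oral capsules as well as the titration doses".

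Core SAP 6.20.1 assigns events to periods by start date: "All of these AE and SAE tables will also be repeated for AEs that are reported with start dates during the IP", and likewise for the maintenance period and the OLP. All patients in the OLP take 1 mg (SAP Section 4), and Addendum Section 3 labels the safety cohorts by the treatment received in the parent study.

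**The concern.** For patients who had placebo, the OLP is the first exposure to RPC1063. For those who had 0.5 mg, it is a dose increase. Aggravation of an existing condition is one form that harm can take on such a step, and the monitored risks include infection, pulmonary events and liver enzyme elevation, where this is plausible. If the OLP tables admit only events that start in the OLP, an infection or dyspnea that began earlier and became worse on 1 mg adds nothing to them. OLP treatment-emergent incidence would then be too low for the cohorts whose exposure has just changed. The core-period and OLP tables would also rest on different definitions under the same name.

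**Working it through.** The plan gives no figure on this point, so the check is a comparison of texts, followed by an illustration of scale.

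**Tracing one event.** Take an AE that starts during placebo treatment, is ongoing at OLP Day 1 and worsens after the first OLP dose. Assume the site keeps a single AE record.

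| Rule | Result for this event |
|---|---|
| Addendum 8: onset from first OLP dose to the 90-day visit | Start date is too early; not counted |
| Core 5.3: onset after first study drug | Treatment-emergent, dated from placebo |
| Core 5.3: worsening after first study drug | Adds nothing; the event already qualifies, and the anchor is the placebo dose (5.4) |
| Core 6.20.1: period tables by start date | Falls in the induction or maintenance table, not the OLP table |
| Core 6.20.1: whole-study table | Counted once at worst severity, with no indication that the worsening came in the OLP |

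For a former 0.5 mg patient the result is the same, with the first 0.5 mg-arm dose as the anchor. So neither the addendum nor the core SAP brings the worsening into the OLP tables.

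**If worsening opens a new AE record.** The new record has a start date in the OLP, the addendum rule captures it, and the loss is nil. SAP 5.3 says that onset dates come from the AE eCRF but does not say which practice applies. Protocol 12.1 does not say either. Protocol 12.4 has events followed until resolved or stabilized, which is compatible with one continuing record. SAP 5.3 names worsening separately from start date, so the plan itself allows for worsening without a new start date.

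**Scale, former placebo patients.** Expected missed patients = n × w, where n is the number entering the OLP and w the share with an ongoing AE that worsens there on an existing record. About 60 patients are randomized per arm (SAP 6.5), so n is at most about 60. The documents give neither the number of entrants nor w, so both ranges are assumptions.

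- Low: 30 × 0.01 = 0.3 patients
- Middle: 45 × 0.05 = 2.25 patients
- High: 60 × 0.10 = 6 patients

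The shortfall in the proportion of the cohort with any OLP treatment-emergent AE is at most w, that is 1 to 10 percentage points under these assumptions. It is less where the patient also has an event that starts in the OLP and is counted anyway.

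**The case against.** The strongest reply has five parts.

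1. *Section 8 says that the events include those with OLP onset, not that they are limited to them, and it is an addendum to v2.0.* The public copy does not show the text of its Introduction or Study Design, so whether Section 8 supplements or replaces 5.3 cannot be seen. This stands as an uncertainty but does not close the gap: if 5.3 still applies, its worsening limb runs from the first study drug dose and its period tables go by start date.

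2. *The addendum did not cause the loss.* This stands. A reader might infer that dropping the worsening limb is the whole fault and that restoring 5.3 word for word would cure it. The tracing above shows that it would not. The anchor has to move to the first OLP dose.

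3. *The events are not hidden.* This also stands. A reader might infer that they are never attributed to active drug, and the documents do not support that. Protocol 12.1 asks the investigator to assess relationship for every AE. SAP 6.20.1 lists all AEs with severity, relationship, seriousness and dates. In the whole-study summaries "the patient is counted once in that preferred term at the maximum severity and closest relationship". Where the treatment received differs from that randomized, SAP 6.8 has patients "analyzed according to the highest dose of RPC1063 actually received and not according to the treatment they are randomized to receive", which could even place a former placebo patient under 1 mg, although the addendum's cohort labels point the other way.

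4. *Laboratory and lung function worsening is measured elsewhere.* This stands in good part. OLP safety data other than AEs use the last assessment before initial RPC1063 as baseline (SAP 5.1). Liver tests have shift tables (6.20.6), and lung function changes are tabulated (6.20.7). What remains is the clinical AE with no such measurement. For a former 0.5 mg patient, moreover, that baseline precedes the 0.5 mg period and does not isolate the dose increase.

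5. *If the eCRF does not date a change in severity, worsening in the OLP cannot be derived.* The AE items named in Protocol 12.1 include no such date. This limits the remedy, which therefore needs a fallback.

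**Conclusion.** The point holds as a gap in the definition of OLP treatment-emergent events. On the visible text, an AE ongoing at OLP Day 1 that worsens on first active exposure or on the higher dose is absent from the OLP treatment-emergent tables unless it was recorded as a new AE. The bias in OLP incidence can only be downward.

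Its size is unknown and probably small: about 0.3 to 6 former placebo patients, assuming 30 to 60 entrants and 1% to 10% with such an event. Former 0.5 mg patients would add to this by a number the documents give no basis for. It is nil if sites always open a new record.

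No efficacy result or hypothesis test is affected, since SAP 6.20 plans no testing of safety data. The change is still worth making because it is cheap and because the OLP tables for these cohorts are where the effect of the new exposure would be looked for.

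**What to change.** In Addendum Section 8, define an OLP treatment-emergent AE as one that meets either condition, through the 90-day follow-up visit:

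- onset on or after the first OLP dose; or
- ongoing at OLP Day 1 and, after the first OLP dose, increasing in severity, becoming serious, or changing from unrelated to related.

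State that this definition replaces SAP 5.3 for the OLP, and state how the eCRF records worsening: as a new AE or as an update to the existing record. Where the change is not dated, flag and list the AEs ongoing at OLP Day 1 with their maximum severity and relationship, by parent-study treatment, so that the possible extra cases are visible even if they cannot be counted.

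The cost is a few sentences, a small change to the derivation of the OLP adverse-event dataset, and possibly one listing. It needs no further patient contact. Reported OLP rates may rise slightly. Where severity changes are undated, the listing gives an upper bound, not a count.

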If the start date of medication is completely missing in which the day, month, and year are all unknown or only the day is known, then the start date will not be imputed.

For the partial start date of medication,

- If the year is present and the month and day are missing or the year and day are present and the month is missing, set month and day to January 1.
- If the year and month are present and the day is missing, set day to 1st day of month.
- If the imputed start date of medication is after the non-imputed end date of medication, then the start date will be set to the end date of medication.

If the end date of medication is completely missing which the day, month, and year are all unknown or only the day is known, then the end date will not be imputed.

For the partial end date of medication,

- If the year is present and the month and day are missing or the year and day are present and the month is missing, set month and day to December 31.
- If the year and month are present and the day is missing, set day to last day of the month.

Adverse Event Dates:

If the adverse event onset date is completely missing, is set to date of first dose.

If year is missing, set it as the year of first dose.

If year is present but (month and/or day) are missing:

- If year = year of first dose, then set missing month and/or day to month and/or day of first dose
- If year < year of first dose, then set missing month and/or day to December and/or 31.
- If year > year of first dose, then set missing month and/or day to January and/or 1.

If month and year are present but day is missing:

- If year = year of first dose and if month = month of first dose, then set day of first dose
- If month < month of first dose, then set day to last day of the month
- If month > month of first dose, then set day to first day of the month
- If year < year of first dose, then set day to last day of the month
- If year > year of first dose, then set day to first day of the month

For all other cases, set to date of first dose.

SPONSOR: CELGENE INTERNATIONAL II SÀRL

Signature of Celgene International II Sarl

100

Representative

[name] Senior Director Global Clinical Trial Management

Printed Name of Celgene International II Sàrl Representative

dd mmm yyyy

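### Open-label AE onset imputation ignores a known end date, so some events that ended before the open-label period are counted as open-label treatment-emergent

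*SAP*

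**What the plan says.** All of the rules at issue are in the OLP addendum to the SAP.

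- **Scope (end of Section 8, introducing Section 9).** "The following missing data imputation rules will be applied to the OLP analyses".
- **AE onset wholly missing (Section 9).** "If the adverse event onset date is completely missing, is set to date of first dose".
- **Year known and matching, month missing (Section 9).** "If year = year of first dose, then set missing month and/or day to month and/or day of first dose".
- **Year and month known and matching, day missing (Section 9).** "If year = year of first dose and if month = month of first dose, then set day of first dose".
- **Catch-all (Section 9).** "For all other cases, set to date of first dose".
- **Medication start (Section 9).** There is a plausibility check against the end date: "If the imputed start date of medication is after the non-imputed end date of medication, then the start date will be set" equal to that end date. The AE rules have no counterpart.
- **OLP treatment-emergence (Section 8).** "Treatment-emergent adverse events include adverse events that started between the date of first dose of OLP and 90-day safety Follow-up visit". The end date plays no part.

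Addendum Section 8 also has AEs recorded from consent onward, so screening, induction and maintenance events are in the same AE data. Main SAP Section 5.3 confirms that AE end dates are collected on the eCRF.

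**The concern.** When an onset date is incomplete, a known end date can still settle whether the event belongs to the OLP. An event that ended before the first OLP dose cannot have started during the OLP. The AE rules do not use this information. They can place the onset on the first-dose date, after the event was over, and Section 8 then classes it as OLP treatment-emergent.

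OLP AE incidence is the long-term safety summary. Every OLP patient receives active drug, and addendum Section 3 labels the cohorts by treatment in the parent study. For the former placebo cohort the OLP is the first active exposure, so an event that began and ended on placebo could be shown as an event on active drug. The medication rule shows that the authors had this kind of check in mind, so its absence from the AE rules looks like an oversight.

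**Working it through.** The plan states no figure for this point, so there is none to reproduce. I applied the rules as written to constructed events, then repeated the exercise with the cap.

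**Notation.** D = date of first OLP dose; S = known AE end date; O = imputed onset.

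- Rule as written, for the three patterns: O = D.
- OLP treatment-emergent if O ≥ D (the upper limit, 90-day follow-up, is not at issue here).
- Capped rule, parallel to the medication rule: O* = min(O, S).

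**General result.** If S < D, the rule as written gives O = D > S, so the event is counted as OLP treatment-emergent. The capped rule gives O* = S < D, so it is not. If S ≥ D, then min(D, S) = D and nothing changes. If S is missing, the cap does not apply and nothing changes.

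**Worked dates (assumed, for illustration).** Core Day 1 is 20 January 2014. Week 8 is Day 64 and Week 32 is Day 232 (protocol Table 1). The OLP must start within 2 weeks of the visit (protocol Section 10.4); I used 7 days.

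- Week 8 non-responder: D = 20 Jan 2014 + 63 + 7 = 31 Mar 2014.
- Maintenance completer: D = 20 Jan 2014 + 231 + 7 = 15 Sep 2014.

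| Patient | Onset recorded | Known end S | O as written | Days O is after S | OLP event as written? | O* with cap | OLP event with cap? |
|---|---|---|---|---|---|---|---|
| Non-responder | nothing | 19 Feb 2014 | 31 Mar 2014 | 40 | yes | 19 Feb 2014 | no |
| Non-responder | 2014 | 19 Feb 2014 | 31 Mar 2014 | 40 | yes | 19 Feb 2014 | no |
| Non-responder | Mar 2014 | 16 Mar 2014 | 31 Mar 2014 | 15 | yes | 16 Mar 2014 | no |
| Completer | nothing | 6 Aug 2014 | 15 Sep 2014 | 40 | yes | 6 Aug 2014 | no |
| Completer | 2014 | 6 Aug 2014 | 15 Sep 2014 | 40 | yes | 6 Aug 2014 | no |
| Completer | Sep 2014 | 8 Sep 2014 | 15 Sep 2014 | 7 | yes | 8 Sep 2014 | no |

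As written, 6 of 6 events that ended before the OLP are counted as OLP treatment-emergent; with the cap, 0 of 6. The cases were built to meet the conditions, so 6 of 6 shows how the rule behaves. It does not estimate frequency.

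**Where the rule works.** If month and year are known, only the day is missing, and the month precedes that of first dose in the same year, Section 9 uses the last day of the known month. An onset of July 2014 in the completer becomes 31 July 2014, before D, and is correctly left out. A known earlier year likewise keeps the event before the OLP.

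**Meaning of first dose.** The Section 9 text does not define it. Three things point to the first OLP dose: the rules are stated to serve the OLP analyses, Section 8 refers to the first dose of the OLP, and addendum Section 6 names the Core Period when it means the core dose.

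**The case against.** The strongest reply is that little will turn on this.

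- **Several conditions must coincide.** The event needs one of the onset patterns above, a known end date, and an end before the first OLP dose. Protocol Section 12.1 has investigators ask at each visit about events since the last one and record when they occurred and how long they lasted. A known end with an unknown onset month should be unusual. The day-missing pattern needs an event that began in the calendar month of the first OLP dose and ended before that dose.
- **The default is reasonable and errs on the cautious side.** Assigning an uncertain onset to the start of active treatment is sensible when the end date is missing or falls on or after first dose.
- **Nothing confirmatory depends on it.** Main SAP Section 6.20 rules out hypothesis testing on safety data.

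All of this stands, and it limits the size of the problem. It does not defend the missing condition: where the end date shows that the event was over, the classification is wrong as well as cautious.

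A reader might infer three stronger things that the documents do not support:

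1. *That every partially dated event in the calendar year of OLP start is misassigned.* The earlier-month rule shows otherwise. Nor is the chance that the core and OLP start dates share a calendar year an error rate.
2. *That the rule fails equally whichever first dose is meant.* The core-dose reading is unlikely on the addendum's own wording. The term merits a definition, but the point does not rest on that ambiguity.
3. *That a duration analysis would be corrupted.* Main SAP Section 5.3 gives a duration formula, but the AE summaries in Section 6.20.1 include none of duration.

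**Conclusion.** The point holds in a narrow form. For three patterns of incomplete onset (wholly missing; year matching with month missing; year and month matching with day missing), addendum Section 9 lets an event known to have ended before the first OLP dose be counted as OLP treatment-emergent. I found nothing in the supplied protocol or SAP that overrides this.

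The direction is toward over-counting in descriptive OLP safety tables. The size cannot be calculated, because neither document gives the number of AEs with incomplete onset and a known earlier end; it is probably small. No efficacy result or test changes.

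The conclusion assumes that first dose means the first OLP dose. The body text of addendum Sections 1 and 2 is not visible in the public copy, so a definition there cannot be excluded. It also assumes that programming follows Section 9 literally. It is a minor but clear error in a stated rule, and worth correcting because the correction is cheap.

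**What to change.** In addendum Section 9, under the adverse event date rules:

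1. State that first dose means the first dose of the OLP.
2. Add that, if the imputed AE onset falls after a non-imputed AE end date, onset is set to that end date, as the medication rule already does. An AE with a known end date before the first OLP dose is then not OLP treatment-emergent.
3. Keep first-dose imputation where the end date is missing or falls on or after the first OLP dose.

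The cost is two or three sentences and a small change to the AE derivation program. No new data are needed, since AE end dates are already on the eCRF.
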